5.2 STUDY PERIODS

Table 3. Study Periods

Period	Start Date	End Date
Screening and Baseline	Date of Signed ICF	Up to Date/Time of First Dose (Exclusive)
Treatment	Date/Time of First Dose	Date of Last Dose
Follow-up	Date after Last Dose +1	Follow-up Visit Date

5.3 DEFINITION OF BASELINE

The following definition of baseline will be used, unless specified otherwise:

- Study baseline will be defined as the last non-missing assessment before first administration of study drug, usually the predose assessment on Day 1

5.4 HANDLING OF DROPOUTS OR MISSING DATA

All available data will be included.

For ANCOVA analyses, patients with missing change from baseline values will be excluded. No imputation will be performed for missing observations.

For responder analyses, all patients will be included. Patients with missing postdose data at an assessment timepoint will be treated as non-responders for that assessment timepoint

All safety and tolerability data will be summarized and analyzed when data values are available for a patient. Data handling for missing dates and other key safety data are described in Section 8.

5.5 INTERIM ANALYSIS AND DATA MONITORING

An independent DMC will be given the responsibility to review trial safety and provide guidance consistent with the objectives of the study and appropriate ethical requirements.

The DMC will comprise recognized experts in cardiovascular disease and one biostatistician who have experience in clinical trials and are not otherwise involved in the conduct of this trial. Their only role in this study will be as a member of the DMC, thus ensuring their independent review of safety data. The detail of DMC is documented in a separate DMC charter.

No additional unblinded interim analyses of efficacy (specified as optional in Protocol Section 5.14) will be performed.

5.6 MULTIPLE COMPARISONS/MULTIPLICITY

Due to the exploratory nature of this study, the analyses will focus primarily on estimation rather than inferential testing. No adjustment on the p-values for multiple testing is planned for this study. All reported p-values are considered nominal. A p-value ≤ 0.05 indicates that the 2 treatment samples are less likely to have been drawn from the same distribution by chance alone.

6. ANALYSIS METHODS

6.1 ANALYSIS POPULATIONS

The following populations will be defined for this study:

- **Screened Population:** All screened patients who have signed the informed consent form for the study and received a patient identification number.
- **ITT Population:** All randomized subjects. Patients in this population will be evaluated according to the treatment group they were assigned to at Randomization. However, all summary tables and efficacy analyses performed on this population will only include the treatment groups (placebo and 40 mg praliciguat) specified in the final amended protocol, unless specified otherwise.
- **Safety Population:** All randomized patients who take at least 1 dose of study drug. The Safety Population will be used for all safety assessments. In the event that a subject receives the wrong treatment, the actual treatment will be used. If a patient received more than 1 treatment, then the patient's data will be summarized according to the treatment they received for the longest duration. All summary tables performed on this population will only include the treatment groups (placebo and PRL 40 mg) included in the final amended protocol, unless otherwise specified.
- **Modified Intent-to-Treat (mITT) Population:** All patients in the ITT Population who take at least 1 dose of study drug and have at least 1 evaluable baseline measurement.
- **Evaluable Population:** All patients in the mITT who complete 8 weeks of dosing (± 3 days) and have at least 1 evaluable postbaseline assessment and did not have a dose reduction. Other criteria, such as major protocol deviations that might have a potential impact on efficacy evaluations (see Section 6.2), may be established and reviewed before database lock and unblinding. The Evaluable Population will be the primary analysis population for the efficacy assessment.
- **PK Population:** All randomized patients who take at least 1 dose of praliciguat and have at least 1 postdose assessment with measurable PK concentration levels.

6.2 PROTOCOL DEVIATIONS

Major protocol deviations will be identified and documented for all randomized patients prior to unblinding through data reviews and programmatic checks of the study data, unless specified otherwise. Major protocol deviations will be determined based on review of all protocol deviations performed by members of the study team, including but not limited to the Sponsor

Medical Monitor and study biostatistician. The categories of major protocol deviations to be reviewed will include, but are not limited to, patients who:

- did not meet the following key inclusion/exclusion criteria
 - inclusion criterion #3 (patients with EF \leq 35%)
 - inclusion criteria #4, 6, 9
 - exclusion criteria # 2, 4, 6, 8
- received disallowed medications postbaseline for \geq 7 days prior to the Week 12 assessment, or received PDE5 inhibitors or nitroglycerine within 72 hours of the Week 12 assessment
- had overall study drug compliance rate \leq 60% in the last 4 weeks of the treatment period or did not have measurable (non-BLQ) plasma concentration levels at the Week 8 and Week 12 predose assessments despite being randomized to praliciguat. The unblinded review of plasma concentration levels to identify such cases will be performed after database lock and study unblinding.
- dosing error likely to impact efficacy outcome measures

The number and percentage of subjects with major protocol deviations will be summarized by type of deviation and by treatment group for the ITT Population. All protocol deviations will be presented in a by-patient listing. Patients randomized to praliciguat 10 mg or 20 mg under Amendment 2 or earlier will not be included in the summary table but will be included in the listing.

6.3 DISPOSITION OF PATIENTS

The number of patients screened and screen-failed, along with the reason for screen failure will be presented for the Screened Population. Categorical summaries of patients randomized, included in each of the analysis populations, who completed the study, or who discontinued early (along with the reasons for discontinuation) will be presented by treatment group for the ITT Population. Subject disposition will also be summarized by investigational site within each geographical region. In addition, by-patient listings of patient disposition, including all patients who failed screening or terminated early, will be presented.

6.4 DEMOGRAPHIC AND BASELINE CHARACTERISTICS

Patient demographics [age, age category, sex, race, ethnicity, weight, height, BMI (defined as weight in kg divided by height in meters squared)], and baseline stratification factors (atrial fibrillation status, baseline peak VO₂ strata) will be summarized by treatment group and overall for the Safety (and ITT, if different), Evaluable, and mITT Populations.

6.5 MEDICAL HISTORY

Medical history, abnormalities and surgeries, reported and occurring prior to screening will be coded using MedDRA version 20.0 or newer. Categorical summaries will be presented by MedDRA system organ class (SOC) and preferred term (PT) by treatment arm and overall for the Safety Population. Patients will be counted once per SOC and PT.

6.6 PRIOR AND CONCOMITANT MEDICATIONS AND PROCEDURES

Prior medications will be defined as medicines taken or procedures performed on the patient prior to the date of first dose of study drug. Concomitant medications and procedures will be defined as medications taken or procedures performed on or after the date of first dose of study drug. Any medication taken or procedures performed after the date of last dose of study drug will not be considered concomitant for the purposes of analysis.

Reported medication will be coded using the World Health Organization (WHO) Drug Dictionary (WHO-DDE B2, Mar 2017 or newer) to their Anatomical Therapeutic Chemical (ATC) class and PT. Categorical summaries for both prior and concomitant medication use for each treatment group will be presented by ATC and PT for the ITT Population. Patients will be counted once per ATC and PT.

6.7 EXPOSURE AND DRUG COMPLIANCE

Exposure to study drug, calculated as the number of days from the first dose taken to the date of the last dose taken, inclusive, will be summarized by treatment group for the ITT Population. The total number of doses taken during the entire study will be calculated for each patient. Patient-years, defined as exposure to the study drug in years, will be summarized by treatment for the ITT Population.

In addition, a frequency table will be provided to display the number and percentage of subjects with exposure in the following categories:

- 1 to \leq 2 weeks (1-14 days),
- >2 to \leq 4 weeks (15-28 days),
- >4 to \leq 8 weeks (29-56 days),
- >8 to \leq 12 weeks (57-84 days), and
- >12 weeks (85 days or more).

Dosing compliance for the treatment period will be defined as the number of doses actually taken by a patient divided by the number of doses that were expected to be taken, multiplied by 100. The total number of doses actually taken will be calculated by subtracting the total number of tablets returned from the total number of tablets dispensed, divided by 2. For patients who had a dose reduction, the total number of actual doses taken from the date of dose reduction will be calculated as the difference between the total number of tablets dispensed and returned. The total number of doses expected to be taken is the number of days between the date of first dose taken and the date of end of treatment visit, inclusive. In addition, drug compliance for the intervals Randomization Visit up to Week 4 Visit, Week 4 Visit up to Week 8 Visit, and Week 8 Visit to Week 12 Visit will be presented. Patients will only be included in the intervals that they were on study (that is, the intervals that are prior to or contain the last dose date). Summaries will be presented by treatment arm and overall for the ITT Population.

Compliance rates will also be categorized as missing, $<60\%$, $\geq60\%$ and $<80\%$, $\geq80\%$ and $\leq120\%$, and $>120\%$ and summarized by treatment group.

6.8 EFFICACY ANALYSES

6.8.1 Baseline Summaries for Efficacy Endpoints

Baseline efficacy parameters including peak VO₂ strata, atrial fibrillation strata, peak VO₂, 6-minute walk test (6MWT), NT-pro BNP, and KCCQ-physical limitations score (PLS), overall summary score (OSS) and clinical summary scores (CSS) will be summarized descriptively by treatment group for the Evaluable Population.

6.8.2 Primary Efficacy Endpoint

6.8.2.1 Definition of Endpoint

The primary efficacy endpoint, change from baseline in peak VO₂, as obtained from CPET at Week 12, will be used to evaluate the effect of praliciguat on peak exercise capacity. CPET measurements will be provided by an independent central CPET Core Lab.

6.8.2.2 Main Analytical Approach

Corresponding with the primary efficacy objective of the trial, the primary inference for hypothesis testing is the treatment difference between the placebo group and the 40 mg praliciguat group on the change from baseline in peak VO₂ at Week 12. The primary efficacy analysis will be conducted using the Evaluable Population using an analysis of covariance (ANCOVA) model with treatment group and atrial fibrillation stratification factor as categorical variable terms and baseline peak VO₂ value as a covariate. The null hypothesis of the test will be interpreted as equality between the placebo and 40 mg praliciguat groups, and rejection of the null hypothesis as evidence that the 40 mg praliciguat group has a greater effect on change from baseline in peak VO₂ than the placebo group. Data for patients randomized to 10 mg praliciguat or 20 mg praliciguat under Amendment 2 or earlier will not be included in the analysis.

Least squares means (LSMs) and 95% confidence intervals for each treatment group as well as LSM difference between the 40 mg praliciguat group and the placebo group will be presented, along with the corresponding confidence intervals and p-values.

Distribution assumptions of the models will be evaluated for evident departure from normality and non-constant variances by examining the model residuals. Upon examination of the model residuals, a suitable data transformation may be applied, and if the results of these analyses show consistency with those obtained from the original analyses, only results from the original analysis will be reported.

6.8.2.3 Additional Analysis of the Primary Efficacy Endpoint

Analysis of the primary efficacy endpoint will also be performed on a subset of the Evaluable Population, excluding patients who had permanent or persistent atrial fibrillation at baseline.

6.8.2.4 Sensitivity/Supportive Analysis

Table 4. Sensitivity/Supportive Analyses of Primary Efficacy Endpoint

Endpoint/Method	Description	Summary Method
mITT Population - LOCF	Repeat primary efficacy analysis using the mITT Population. A last-observation-carried-forward (LOCF) approach will be used to impute missing Week 12 assessments of change from baseline in peak VO ₂ . Under the LOCF approach, the patient's previous value during the Treatment Period from Week 8 or earlier postbaseline assessments will be used in case of missing Week 12 assessments. In the case of premature discontinuation from the trial, the patient's last available value during the Treatment Period will be used. If no previous postdose value exists, a change-from-baseline value of "0" will be imputed.	Continuous Summary ANCOVA results for Week 12
Subset of mITT-LOCF	Repeat the mITT LOCF analysis on a subset of the mITT Population, excluding patients who had permanent or persistent atrial fibrillation at baseline	Continuous Summary ANCOVA results for Week 12
Evaluable Population With other covariates	If baseline imbalances are apparent for other parameters, include them in the model to adjust for variability	ANCOVA results for Week 12
Evaluable Population including geographic region	Repeat primary efficacy analysis including geographic region, as defined in Appendix 4 - Table 10, in the ANCOVA model.	Continuous Summary ANCOVA results for Week 12
Evaluable Population - Rank Transform	Performed only if there is evidence of non-normality. Change and baseline values will be ranked based on the normalization method of Blom with ties set to the mean. If the results of the sensitivity analysis show consistency with those obtained from the original analysis, only results from the original analysis will be reported.	
MMRM – Evaluable Population	Perform a mixed-effects model repeated measures (MMRM) analysis with change from baseline in peak VO ₂ as the response variable, treatment, visit, treatment-by-visit interaction, and baseline atrial fibrillation status as fixed effects and baseline peak VO ₂ as the covariate with unstructured as the variance-covariance structure. All available data will be included in the analysis. Please see code in Appendix 5.	Continuous Summary MMRM results

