5.9.2 Analyses on the Primary Efficacy Endpoint

An ANCOVA analysis as described in Section 5.1.1 will be performed on the primary efficacy endpoint as defined in Section 4.1.2 with treatment group and stratification factors as categorical variable terms and the corresponding baseline CPET value as a covariate on each of the following 2 populations:

- Evaluable Population
- A subgroup of the Evaluable Population, excluding patients who had permanent or persistent atrial fibrillation at baseline

Sensitivity analyses similar to the above analysis will be performed on each of the above 2 analyses using the mITT Population. In these analyses, patients without a Week 12 CPET measurement will carry Week 8 or earlier postbaseline measurement forward. Patients with no postbaseline CPET measurement will be assigned 0 as improvement, or no change from baseline. Details of the sensitivity analysis will be included in the SAP.

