4. DETERMINATION OF SAMPLE SIZE

The study is not designed to formally test a single statistical hypothesis; however, approximately 184 subjects will provide approximately 90% power to detect a mean difference of 1.3 (mL O₂/kg/min) between the 40 mg praliciguat treatment arm and the placebo treatment arm in change from baseline at Week 12 peak VO₂. This estimate is based on the Evaluable Population (defined in Section 6.1), including patients with permanent or persistent atrial fibrillation at Screening, and using the follow assumptions:

- 5% Type I error for a 2-sided test
- Mean Peak VO₂ change from baseline at Week 12 for Placebo arm is 0.0 (mL O₂/kg/min)
- Mean Peak VO₂ change from baseline at Week 12 for 40 mg praliciguat is 1.3 (mL O₂/kg/min)
- Equal standard deviation for all treatment arms at 2.5 (mL O₂/kg/min) for change from baseline at Week 12
- 10% attrition prior to Week 12 CPET
- 10% of the total number of patients were randomized to either the 10 or 20 mg praliciguat dose groups under Amendment 2 of the protocol (or earlier)
- Reduced treatment effect for praliciguat in subjects with permanent or persistent atrial fibrillation at Screening

Additionally, under similar assumptions, this sample size will also provide 90% power to detect a mean difference of 1.5 (mL O₂/kg/min) on the same endpoint on the well-defined subgroup of a minimum of approximately 148 patients without permanent or persistent atrial fibrillation at Screening.

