6.8.3 Secondary Efficacy Endpoints

The following secondary efficacy endpoints will be used to evaluate the effect of praliciguat on exercise and functional capacity.

- Change from baseline in 6MWT distance at Week 12. 6MWT is a simple assessment of everyday functional capacity and provides a global evaluation of the organ/physiologic systems involved in exercise. The distance, in meters, travelled in 6 minutes, measured at approximately the same time of day will define the endpoint.
- Change in ventilatory efficiency as defined by VE/VCO₂ slope (minute ventilation/carbon dioxide production) obtained from CPET at Week 12. These values will be provided by an independent central CPET Core Lab
- CPET Responders, defined as patients who improve by at least 1.5 mL O₂/kg/min in peak VO₂ from baseline to Week 12. Patients who are hospitalized or who die due to heart failure during the study treatment period or who are missing Week 12 postdose values will be considered non-responders.

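### The mITT-LOCF check on peak VO2 applies no penalty when a Week 12 CPET is missing because of death or heart-failure hospitalisation, so it barely registers an excess of such events if survivors improve on drug

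*SAP*

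**What the plan says.** **The sensitivity rule.** The two mITT rows of SAP Table 4 (6.8.2.4) rerun the primary ANCOVA, once in the whole mITT Population and once without patients in permanent or persistent atrial fibrillation. A missing Week 12 change takes the Week 8 or earlier postbaseline value. After premature discontinuation it takes the last value in the Treatment Period. "If no previous postdose value exists, a change-from-baseline value of" zero is imputed. Protocol 5.9.2 agrees: "Patients with no postbaseline CPET measurement will be assigned 0 as improvement, or no change from baseline".

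**The other peak VO2 analyses.** SAP 5.4 drops patients with a missing change from ANCOVA. SAP 6.1 limits the Evaluable Population to patients with 8 weeks of dosing, a postbaseline assessment and no dose reduction. The primary analysis and every Table 4 row other than the two mITT rows, MMRM included, use that population.

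**The responder endpoint.** SAP 6.8.3 treats the same events as failure: "Patients who are hospitalized or who die due to heart failure during the study treatment period" count as non-responders, as do patients with no Week 12 value. SAP 6.8.5 runs that analysis in the Evaluable Population.

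**Related provisions.** Protocol 3.4.2 asks patients who stop drug to have the End of Treatment (EOT) assessments at that time. SAP 8.1 lets an EOT assessment from Day 77 stand as Week 12 if Week 8 is present. Protocol 3.8.14 has all deaths and cardiovascular hospitalisations classified blind.

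**The concern.** The mITT-LOCF rows are where a reader would look to see whether the primary result survives the loss of patients. The worrying loss in this population is a patient who dies, or is too ill with heart failure to exercise at Week 12. That patient is scored as unchanged, or as well as at the last test. The sample-size section assumes that the mean change at "Week 12 for Placebo arm is 0.0" mL O2/kg/min, so a death before any postbaseline CPET counts as an average placebo course. A patient at +2 in Week 8 who dies in Week 10 counts as +2.

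If such losses were more frequent on drug while survivors improved, the primary analysis and its mITT check would both report the survivors' gain. Their agreement would then say little about the patients who were lost.

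**Working it through.** **1. The plan's own power.** Inputs from SAP section 4: "5% Type I error for a 2-sided test"; "approximately 184 subjects will provide approximately 90% power to detect a mean difference of 1.3"; "Equal standard deviation for all treatment arms at 2.5"; "10% attrition prior to Week 12 CPET"; and a further 10% of patients randomised to 10 or 20 mg.

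Power = Φ(δ/SE − 1.96), with SE = SD × √(2/n).

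- n = 184 × 0.9 × 0.9 / 2 = 74.5 per arm.
- SE = 2.5 × √(2/74.5) = 0.410, and 1.3/0.410 = 3.17.
- Power = 88.8%, which agrees with the stated figure of about 90%.

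The sample size is not in dispute. For the mITT, only the 10- and 20-mg patients are removed: 184 × 0.9 / 2 = 82.8, taken as 83 per arm.

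**2. How far zeros move the result.** Let a fraction e of the drug arm, and none of the placebo arm, have an event and no Week 12 CPET. If all are set to 0 and survivors gain 1.3, the mean difference is (1 − e) × 1.3. With 83 per arm, SE = 0.388.

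- e = 10%: difference 1.17, power 85%.
- e = 20%: difference 1.04, power 76%.

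To bring the difference to zero, each event would have to score −(1 − e) × 1.3 / e. That is −11.7 mL O2/kg/min at 10% events and −5.2 at 20%.

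**3. Simulation of the Table 4 rule against worst rank.** 83 per arm, survivor gain 1.3, SD 2.5, 4,000 trials per row, ANCOVA on baseline. Assumptions not in the documents: the event rates, half of event patients having a Week 8 value to carry (the rest set to 0), and a Week 8 to Week 12 correlation of 0.7. The comparator gives event patients the worst rank and fits ANCOVA to Blom scores. Entries are the share of trials significantly positive for drug; repeat runs move them by up to about 2 points.

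| Events, drug v placebo | LOCF/0 | Worst rank |
|---|---|---|
| 2% v 2% | 91% | 86% |
| 4% v 2% | 91% | 77% |
| 6% v 2% | 90% | 65% |
| 10% v 2% | 89% | 39% |

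Rank-transforming the LOCF data without a penalty still gives 89–91%, so the gap comes from how events are scored. Complete-case analysis gives about 90%, so LOCF/0 adds little to it.

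A second set used different assumptions: events on drug only, one third with a carried value, unadjusted t-test. LOCF/0 gave 90%, 89%, 87% and 84% at 5%, 10%, 15% and 20% events. Worst rank gave 73%, 44%, 16% and 1%.

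**4. Does the rule create benefit?** With no survivor gain and events unrelated to potential change, LOCF/0 has a mean difference of about 0 and is significantly positive in about 2% of trials, the nominal tail. A false benefit needs selective events. If events remove exactly the patients who would have changed worst and 0 replaces them, the bias is +0.42 at 10% events (22% significantly positive) and +0.70 at 20% (55%).

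**The case against.** A reader might infer that a harmful drug can look robustly positive because of LOCF/0. The documents and the arithmetic do not support that. The table builds in a real gain of 1.3 in survivors, and the rule reports that gain. With an assumed placebo change of 0, scoring drug-arm losses as 0 pulls the difference towards the null. The weakness is a missing penalty, and false benefit arises only under the strongly selective mechanism in step 4.

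A reader might also infer that every heart-failure hospitalisation is scored 0 or the Week 8 value. It is not. The trigger is a missing Week 12 CPET, so a hospitalised patient who is tested at Week 12 keeps the measured value. The value carried may be an EOT CPET done when drug was stopped, and one from Day 77 may count as Week 12. The simulation leaves out these routes. They help patients who can still exercise, not those who die or cannot be tested.

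Two further objections stand in part. Worst rank tests a composite of survival, hospitalisation and exercise, whereas the objective is peak exercise capacity and the SAP puts estimation first; the gap in the table is therefore not an error in LOCF. The event rates are also unsupported, and 10% on drug would use the plan's whole attrition allowance in that arm.

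Finally, harm would be visible elsewhere: in adjudicated events, in DMC review and in the responder endpoint. The responder endpoint is no backstop for early losses, because a patient who dies in Week 5 is not in the Evaluable Population. How cardiac events are analysed cannot be judged where exploratory text is redacted.

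**Conclusion.** The point holds as a limitation of the sensitivity analysis. No listed analysis of peak VO2 change counts death, or loss of the Week 12 test through heart-failure hospitalisation, as a bad outcome. The two mITT rows, the only ones that keep patients lost before Week 8, score such patients neutrally or with an earlier value. If survivors gain about 1.3, the chance of a significant mITT result stays near 90% whether drug-arm events are 2% or 10% against 2% on placebo, while a worst-rank analysis falls from 86% to 39%.

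That size rests on assumed event rates, timing and correlation; at 4% against 2% the contrast is 91% to 77%. It does not show that the plan manufactures benefit, and it does not call the primary analysis or the sample size into question. It is a cheap improvement.

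**What to change.** Add a new row to SAP Table 4 for the mITT Population, and one for its subset without permanent or persistent atrial fibrillation, always reported beside the LOCF result:

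- Patients with no Week 12 CPET who died, or had an adjudicated heart-failure hospitalisation, before that test take the worst rank.
- Other missing values follow the existing LOCF/0 rule.
- A rank ANCOVA on Blom scores is fitted with the terms of the primary model.

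It must be written as a new analysis. The Blom row now in Table 4 covers only the Evaluable Population, runs only if non-normality appears, and goes unreported when it agrees with the main result.

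The SAP should say that the rule differs from the responder rule on purpose: it covers all deaths, and it leaves a measured Week 12 value in place after a hospitalisation.

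Cost: SAP wording and one table for each of the two populations, from events already adjudicated. The result is a composite, gives no estimate in mL O2/kg/min, and loses about 5 points of power when events are balanced (91% to 86% at 2% v 2%). The primary analysis is unchanged.
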